## 6. ANALYSES AND SUMMARIES

### 6.1. Primary Endpoint(s)

#### 6.1.1. Percent Change From Baseline in Non-HDL-C at Week 24

##### 6.1.1.1. Main Analysis

- Estimand strategy: Hypothetical (Section 2.1.1).
- Analysis set: FAS\_primary (Section 4.1).
- Analysis methodology: MMRM (Section 5.2.1).
- Intercurrent events and missing data: All off-treatment data (ie, occurring at least 1 dosing interval after discontinuation of treatment), or data collected post treatment of severe hypertriglyceridemia (Section 2.1.1), if collected, will be excluded from analysis.
- The sample size, mean, standard deviation, median, minimum, and maximum at the baseline and post-baseline visits for observed non-HDL-C values and percent change from baseline will be presented for each treatment arm.
- The least-squares (LS) means, the 95% confidence interval for the LS means, the difference in the LS means between each dose group of the vupanorsen and the placebo, its corresponding 95% confidence interval and p-value will be presented.

##### 6.1.1.2. Sensitivity/Supplementary Analyses

###### Supplementary Analysis

Three supplementary analyses, with two using the treatment policy estimand strategy, and one using the principal stratum estimand strategy (Section 2.1.3) will be conducted to provide additional support and context for the primary analysis. The first two will be MMRM model and the MI-RD approach applied to the analysis set of FAS respectively. While the last one will be a two-step regression approach (Section 5.2.1.1) applied to the set of FAS\_ps (Section 4.4).

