### 2.1.3. Additional Estimand(s)

#### Estimands of supplementary analyses

In many settings due to intolerance or inadherence, such as discontinuation of treatment or initiation of an add-on therapy when pre-specified criteria are met, including all data collected in the analysis will violate the assumption of the hypothetical estimand.

Following the estimand theory, as detailed in [1], the following two additional estimands will be used for supplemental analyses of primary and key secondary endpoints (ie, at Week 24). The treatment policy estimand estimates the between-group difference of treatment effect without regard to tolerance or adherence to the randomized treatment (eg, receipt of treatment for severe hypertriglyceridemia). The principal stratum

estimand estimates the between-group difference of treatment effect, restricted to the stratum that subjects who adhere to their randomized vupanorsen groups, but regardless of adherence to the placebo group (ie,  $S_{*+}$  in [2]).

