#### 5.2. General Methods

##### 5.2.1. Analyses for Continuous Endpoints

Continuous endpoints will be summarized using the following descriptive statistics: number of subjects, arithmetic mean, standard deviation, median, minimum, maximum. Other descriptive statistics such as standard error, 1st quartile, 3rd quartile, IQR, etc. will

be added where appropriate. They will be summarized and tabulated by treatment groups and visits (including the 12-week safety follow-up visits when available), for the observed data and (percent) change from baseline.

For graphical summaries, mean +/- standard error, LS-Mean +/- standard error will be plotted for the observed data, (percent) change from baseline over time by treatment groups.

For statistical efficacy analyses, an MMRM model featuring the hypothetical estimand will be applied to primary and secondary endpoints, as primary analyses. All eligible post-baseline visits up to and including the analysis visit will be included in the MMRM model, in which baseline value, treatment (categorical), visit (categorical) and interaction term of treatment (categorical) by visit (categorical) will be treated as fixed effects and an unstructured covariance matrix will be used to account for the correlation among visits. If a model convergence issue is encountered with unstructured covariance matrix, then a simpler covariance structure, such as Toeplitz or compound symmetry will be considered. The restricted maximum likelihood (REML) method along with Kenward-Roger adjustment for degrees of freedom will be used for parameter estimation.

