### 5.3. Methods to Manage Missing Data

The missing data of the primary hypothetical estimand are defined as all visits post occurrence of intercurrent events (Section 2.1.1). In the primary analysis, due to its inherent assumption of missing at random (MAR), no explicit imputation is needed. The following return to baseline (RTB) sensitivity analysis will be conducted to further evaluate the robustness of the primary results, by using a specific MNAR assumption to impute the missing data of Week 24. Then we will introduce the MI-RD supplementary analysis, as it's the only approach that explicitly imputes missing data, out of all three supplementary analyses.

The RTB missing data sensitivity analysis will be implemented on the same analysis set and hypothetical estimand as the primary analysis, but with a varied assumption, to assess how robust the primary results are. The RTB approach assumes for subjects with missing values at Week 24, their values at Week 24 should eventually return to around their baseline level, ie, their values at Week 24 will be imputed using a normal distribution with the baseline level as the mean and the mean squared error (MSE) from ANCOVA model excluding subjects with missing Week 24 values as the variance. A total of 100 imputations will be performed and each dataset will be analyzed using ANCOVA adjusting for baseline value and treatment group (categorical), then all 100 results will be combined into a single estimate following Rubin's rules [3].

The MI-RD approach serves as additional evaluation of the primary results, along with the other two supplementary analyses. It defines missing data differently, due to the TP estimand it represents. More specifically, it includes data collected post occurrence of intercurrent events in the analysis, and therefore its missing data scope is smaller than the hypothetical estimand. This approach assumes subjects who discontinue the study are expected to have similar values of endpoints, compared to those in the same treatment group that agree to stay in the study for safety follow-up after treatment discontinuation ("retrieved dropouts"), after adjusting for values of baseline visit and last on-treatment visits. The imputation is implemented within groups defined by treatment groups. The missing values at Week 24 are imputed with baseline, last on-treatment visit as predictors, using a regression-based MI approach. The imputation dataset only contains

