subjects with missing values of Week 24, together with retrieved dropouts. After a total of 100 datasets are imputed, each completed dataset consisting of all subjects will be analyzed using ANCOVA adjusting for baseline, treatment group. Then all 100 results will be combined into a single estimate [3]. Note if this method is not fully applicable, eg, no sufficient RDs to impute the missing values in one treatment group, then this supplementary analysis might not be produced.

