## 9. APPENDICES

### Appendix 1. Summary of Efficacy Analyses

Endpoint	Analysis Type	Estimand	Population	Data Inclusion and Rules for Handling Intercurrent Events and Missing Data	Analysis Model	Explicit Imputation
Percent change from baseline in non-HDL-C at Week 24	Main analysis	Hypothetical	FAS_primary	Data collected post occurrence of intercurrent events will be excluded from analysis.	MMRM	N
Percent change from baseline in non-HDL-C at Week 24	Supplementary analysis	Principal Stratum	FAS_ps	All data collected in the placebo group will be included regardless of intercurrent events; Subjects who experience intercurrent events in the vupanorsen groups will be excluded from analysis.	The principal stratum estimand approach	N
Percent change from baseline in non-HDL-C at Week 24	Supplementary analysis	TP	FAS	All data collected will be included regardless of intercurrent events	MMRM	N
Percent change from baseline in non-HDL-C at Week 24	Supplementary analysis	TP	FAS	All data collected will be included regardless of intercurrent events	MI-RD	Y
Percent change from baseline in non-HDL-C at Week 24	Sensitivity analysis	Hypothetical	FAS_primary	Data collected post occurrence of intercurrent events will be excluded from analysis.	RTB	Y
Percent change from baseline in non-HDL-C at Week 24	Dose-response analysis	NA	FAS_primary	Data collected post occurrence of intercurrent events will be excluded from analysis.	Bayesian Emax	N
Percent change from baseline in TG at Week 24	Main analysis	Hypothetical	FAS_primary	Data collected post occurrence of intercurrent events will be excluded from analysis.	MMRM	N
Percent change from baseline in TG at Week 24	Supplementary analysis	Principal Stratum	FAS_ps	All data collected in the placebo group will be included regardless of intercurrent events; Subjects who experience intercurrent events	The principal stratum estimand approach	N

Endpoint	Analysis Type	Estimand	Population	Data Inclusion and Rules for Handling Intercurrent Events and Missing Data	Analysis Model	Explicit Imputation
				in the vupanorsen groups will be excluded from analysis.		
Percent change from baseline in TG at Week 24	Supplementary analysis	TP	FAS	All data collected will be included regardless of intercurrent events	MMRM	N
Percent change from baseline in TG at Week 24	Supplementary analysis	TP	FAS	All data collected will be included regardless of intercurrent events	MI-RD	Y

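### The FAS MMRM is labelled treatment policy, but it gives largely on-drug Week 24 values to participants who stop drug and leave the study, and the analysis that models them as off drug may be dropped with no named fallback.

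*SAP*

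**What the plan says.** SAP 2.1.3 defines the target: "The treatment policy estimand estimates the between-group difference of treatment effect without regard to tolerance or adherence to the randomized treatment". Sections 5.2.1 and 6.1.1.2 and Appendix 1 assign two analyses to it for non-HDL-C and the key secondary endpoints at Week 24: "The first two will be MMRM model and the MI-RD approach applied to the analysis set of FAS respectively". For both, Appendix 1 gives the data rule "All data collected will be included regardless of intercurrent events", but it marks explicit imputation as no for the MMRM and yes for MI-RD.

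The MMRM is specified once, in 5.2.1: "baseline value, treatment (categorical), visit (categorical) and interaction term of treatment (categorical) by visit (categorical) will be treated as fixed effects". The example code in Appendix 4 matches. On missing data, 5.3 says: "In the primary analysis, due to its inherent assumption of missing at random (MAR), no explicit imputation is needed". That sentence concerns the primary run, but the FAS run uses the same model. Of MI-RD, 5.3 says that "it's the only approach that explicitly imputes missing data, out of all three supplementary analyses". MI-RD assumes that study leavers resemble same-arm participants who stopped drug but stayed. If an arm has too few of these, "then this supplementary analysis might not be produced". No substitute is named.

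A return-to-baseline (RTB) sensitivity analysis is also planned, under the hypothetical estimand. Section 6.1.1.2 puts it on FAS. Section 5.3 (by reference to the primary analysis set) and Appendix 1 put it on FAS_primary.

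Protocol 7, 7.1.2 and 7.2.1 and footnote g of the Schedule of Activities keep participants who stop drug on scheduled visits unless they withdraw consent.

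**The concern.** FAS brings in off-drug values only where they were collected. A participant who stops drug and leaves contributes mainly on-drug values, and nothing in the model records that drug was stopped. The MMRM fills the gap from those values and from an arm-by-visit mean made up mostly of people still on drug. For these participants that is the stay-on-drug assumption of the primary estimand, whereas treatment policy calls for an off-drug value. Placebo leavers have no drug effect to lose, so the error does not cancel between arms.

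MI-RD makes the contrary assumption about the same people, so one label covers two incompatible assumptions. If MI-RD is not produced, the MMRM is the only treatment-policy result. Its closeness to the primary estimate could then be read as robustness to stopping treatment when part of it comes from a shared assumption. The study's stated purpose is effect estimation and dose selection, so this matters most if leaving differs by dose.

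**Working it through.** **Inputs from the documents.** SD 17.5, treatment discontinuation 15%, planning effect -20% and 20 per arm (Protocol 9.2); 35% reduction (Protocol 4.3); terminal half-life 3 to 5 weeks (Protocol 2.2.4.1); arms of 20 and 40 (SAP Table 1).

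**Assumptions.** Share of stoppers who leave, 0 to 100%; effect off drug lost at once, or with a half-life of 4 or 8 weeks; within-person correlation 0.6; last on-treatment visit equally likely at Week 4, 8, 12, 16 or 20; same stopping rate in both arms; placebo change zero. The documents give no study-withdrawal rate and no rate at which the lipid effect is lost.

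**The plan's own figure.** n = 20 × 0.85 = 17. Half-width = 1.96 × 17.5 × √(2/17) = 11.76. Power at a difference of 20 = 91.5%. Both reproduce.

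**True treatment-policy value at -20%, 4-week half-life.** The on-drug effect is taken to build up as -20 × (1 - 0.5^(t/4)) / (1 - 0.5^6), giving -10.2, -15.2, -17.8, -19.0 and -19.7 at the five stopping visits. The fractions left at Week 24 are 1/32, 1/16, 1/8, 1/4 and 1/2. The mean off-drug value is -(0.3 + 1.0 + 2.2 + 4.8 + 9.8)/5 = -3.6. The true difference is 0.85 × (-20) + 0.15 × (-3.6) = -17.5.

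**What the FAS MMRM gives.** Simulation with 200,000 per arm, visits at Weeks 4 to 24, and the maximum-likelihood estimate under dropout obtained by sequential regression with arm-specific intercepts and common slopes. Overstatement, in percentage points:

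| Stoppers leaving | -20%, lost at once | -20%, 4 wk | -20%, 8 wk | -35%, lost at once | -35%, 4 wk | -35%, 8 wk |
|---|---|---|---|---|---|---|
| 0% | 0 | 0 | 0 | 0 | 0 | 0 |
| 25% | 0.67 | 0.54 | 0.45 | 1.19 | 0.97 | 0.74 |
| 50% | 1.40 | 1.15 | 0.91 | 2.46 | 2.00 | 1.58 |
| 75% | 2.20 | 1.77 | 1.39 | 3.84 | 3.14 | 2.46 |
| 100% | 3.04 | 2.44 | 1.98 | 5.24 | 4.33 | 3.40 |

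**Cross-check.** Overstatement = share stopping × share leaving × (true off-drug mean minus the value the model implies). With half leaving at -20% and 4 weeks, the implied leaver value is -3.6 - 1.15/(0.15 × 0.5), about -19: nearly the full on-drug effect. If all leave and the effect is lost at once, the ceiling is 0.15 × 20 = 3.0, or 0.15 × 35 = 5.25.

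**Sensitivity, same case.** Correlations of 0.3 and 0.8 both give about 1.1 points. If leavers provide one off-drug visit before going, it is about 0.8.

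**Can MI-RD be fitted?** A regression on baseline and last on-treatment value has three coefficients, so at least 4 retrieved dropouts are needed to estimate a residual variance. With 15% stopping and half of them staying, each participant is a retrieved dropout with probability 0.075. P(at least 4) is 5.8% in an arm of 20 and 35% in an arm of 40.

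**What RTB gives.** With every stopper's Week 24 value set to baseline (FAS_primary): 0.85 × (-20) = -17.0, against a true -17.5. On FAS with half retrieved: -17.0 + 0.075 × (-3.6) = -17.3.

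**The case against.** The strongest reply is that the plan already surrounds this analysis with others. MI-RD targets exactly these leavers. RTB carries no clause allowing it to be dropped, and it falls slightly on the conservative side of treatment policy. That stands in large part: a reader of the whole report would see a less favourable number. But RTB is assigned to the hypothetical estimand and its analysis set is stated inconsistently, so it does not serve as the treatment-policy result when MI-RD is missing.

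Second, the FAS MMRM does what the treatment-policy definition in SAP 2.1.3.1 asks with collected data, and handling of uncollected data is a separate assumption. This is fair, but that assumption is not stated for this analysis, and it contradicts the one made for MI-RD under the same label.

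Third, a reader might infer that the MMRM necessarily overstates the effect. The documents do not support that. The protocol keeps stoppers on the visit schedule, an early-termination visit with a lipid panel is planned, and the 15% is a rate of stopping treatment, not of leaving. With complete follow-up the error is zero. Nor do the documents show that high-dose arms will lose more participants. Treatment and study discontinuations will be tabulated by arm, so any imbalance will be visible.

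Fourth, 1.2 points is about a tenth of the planned ±11.76 half-width, in a supplementary analysis of an exploratory study with no formal decision rules. This limits the weight of the point but does not remove it.

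**Conclusion.** The point holds conditionally. The FAS MMRM estimates the treatment-policy effect only to the extent that stoppers are measured at Week 24. For those who leave, it reverts to a largely on-drug value. The overstatement is 0 to about 3 points at -20% (about 1.2 if half of stoppers leave) and 0 to about 5 points at -35%. These ranges rest on the 15% discontinuation rate and on assumed leaving and decay rates. The plasma half-life is only a guide to how fast the lipid effect fades.

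The firmer defect is structural: the treatment-policy analysis suited to leavers may be dropped, quite plausibly in arms of 20, and nothing is named in its place. A reader might go further and conclude that the primary result is biased. It is not affected by this point, because on-drug values for leavers are what the hypothetical estimand targets. The change is worth making because it is cheap, but the trial's main conclusion does not depend on it.

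**What to change.** Amend SAP 5.3, 6.1.1.2 and Appendix 1:

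- Make the imputation-based analysis on FAS the treatment-policy analysis. Keep all observed values on and off treatment. Impute Week 24 values missing after drug was stopped by MI-RD, and those missing while on treatment under MAR. Analyse with the planned ANCOVA and Rubin's rules.
- Pre-specify a minimum number of retrieved dropouts per arm. If any arm falls below it for an endpoint, use the return-to-baseline draw of 5.3 for post-discontinuation missing values in all arms for that endpoint. A switch made arm by arm would mix assumptions across doses.
- Keep the FAS MMRM as a descriptive analysis and relabel its Appendix 1 rows 'all observed data, MAR'.
- State one analysis set for the existing RTB sensitivity analysis.

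The cost is SAP wording, reusing imputation code that is already needed, with no new data. When the fallback is used, the supplementary estimate will be somewhat conservative and slightly less favourable, since return to baseline ignores residual effect of a drug with a long half-life. On the counts above, a minimum of 4 would trigger the fallback often, so it should be written as a full analysis and not as a remote contingency.

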## Sensitivity Analyses

To assess the robustness of the primary analysis, the RTB analysis based on the primary estimand but an assumption of MNAR will be conducted ([Section 5.3](#)), using the FAS analysis set.

For each supplementary/sensitivity analysis, the least-squares (LS) means, the 95% confidence interval for the LS means, the difference in the LS means between each dose of vupanorsen and placebo, its corresponding 95% confidence interval and p-value will be presented.

### **6.2. Secondary Endpoint(s)**

#### **6.2.1. Percent Change From Baseline in TG, ApoB, LDL-C, ANGPTL3 at Week 24**

##### **6.2.1.1. Main Analysis**

Same as primary endpoint ([Section 6.1.1.1](#)).

##### **6.2.1.2. Sensitivity/Supplementary Analysis**

Same as primary endpoint ([Section 6.1.1.2](#)).

#### **6.2.2. Percent Change From Baseline in Non-HDL-C, TG, ApoB, LDL-C, ANGPTL3 at Week 16**

Only summary statistics and mean plot (Mean +/- SE) over time will be produced.

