### 2.1.2. Secondary Estimand(s)

The primary estimand of secondary endpoints will follow the hypothetical estimand approach to estimate the effect of treatment under the hypothetical condition that all participants maintained their randomized treatment through Week 16 or 24 (as indicated below in Variable). This estimand is meant to estimate the pharmacological effect of the drug when taken as directed. It includes the following 4 attributes:

- Population: Patients with dyslipidemia taking a statin who meet the inclusion/exclusion criteria.
- Variable:
  - Percent change from baseline in TG, ApoB, LDL-C, non-HDL-C, ANGPTL3 at Week 16;
  - Percent change from baseline in TG, ApoB, LDL-C, ANGPTL3 at Week 24.
- Intercurrent event: All off-treatment data (ie, occurring at least 1 dosing interval after discontinuation of treatment), or data collected post treatment of severe hypertriglyceridemia (ie, change in statin dose or addition of TG lowering therapy; Section 8.2.7 of the protocol), if collected, will be excluded from analysis.
- Population-level summary: Difference of variable means between PF-07285557 and placebo.

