#### 5.1. Hypotheses and Decision Rules

The null hypothesis for the primary endpoint is:

$H_0$ : There is no difference in mean percent change from baseline in non-HDL-C at Week 24 between vupanorsen and placebo.

The study objective is treatment effect estimation and dose selection and therefore no formal decision rules for inferential purposes are planned. Each vupanorsen treatment group will be compared to the pooled placebo group, ie, placebo-adjusted LS-mean treatment effect for each dose will be reported along with 95% CI and p-value without adjustment for multiple comparisons to placebo.

The Mixed Model Repeated Measurements (MMRM) will be used as the primary statistical method to estimate the difference of treatment effect between each dose of vupanorsen versus placebo at Week 24. Statistical inference including effect size, p-value, 95% CI will be presented for primary and secondary endpoints respectively, with no adjustment for multiplicity.

Although an interim analysis will occur at Week 16, no formal hypothesis testing nor statistical inference will be conducted.

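### SAP 6.2.2 restricts the five Week 16 secondary endpoints to descriptive output, although SAP 2.1.2 and 5.2.1 define and plan a model-based difference from placebo

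*SAP*

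**What the plan says.** SAP 3.2 lists nine secondary endpoints, five of them at Week 16. SAP 2.1.2 names those five as variables of the secondary estimand, "Percent change from baseline in TG, ApoB, LDL-C, non-HDL-C, ANGPTL3 at Week 16", under the hypothetical strategy, and closes with "Population-level summary: Difference of variable means between PF-07285557 and placebo".

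On method, SAP 5.2.1 states that "an MMRM model featuring the hypothetical estimand will be applied to primary and secondary endpoints, as primary analyses", and adds that "All eligible post-baseline visits up to and including the analysis visit will be included in the MMRM model". SAP 5.1 says that "Statistical inference including effect size, p-value, 95% CI will be presented for primary and secondary endpoints respectively". SAP 4.1 makes FAS_primary the primary analysis set for secondary endpoints.

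The endpoint-specific text splits by visit. SAP 6.2.1 gives the four Week 24 secondary endpoints the same main analysis as the primary endpoint. SAP 6.2.2, for the five Week 16 endpoints, reads in full: "Only summary statistics and mean plot (Mean +/- SE) over time will be produced".

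Protocol 9.4.1 calls for each dose to be compared with placebo on the secondary endpoints. Protocol 9.4.3 asks for placebo-adjusted LS means with CI and p-value at a list of visits that includes Week 16.

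**The concern.** An estimand whose population summary is a between-group difference needs an estimator of that difference. The restriction to descriptive output in 6.2.2 removes it for all five Week 16 variables. Two programmers, one working from 5.2.1 and the other from 6.2.2, would deliver different tables.

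Arm means with standard errors would remain, so a reader could form a crude contrast. That contrast would have neither the baseline adjustment nor the missing-at-random handling of excluded visits that the MMRM provides. Timing also matters. Under SAP Section 5 the sponsor is unblinded once all participants have reached Week 24 or left the study. If the conflict is still open then, the decision whether to report Week 16 contrasts, and from which model fit, could be made with results in hand.

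**Working it through.** This is a conflict of text. The documents give no precision or power figure for Week 16. The ±11.76% in protocol 9.2 concerns Week 24 non-HDL-C. It reproduces as 1.96 × 17.5 × √(2/17) = 11.76, with 20 × 0.85 = 17 completers per arm, and plays no further part here.

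**Does 5.2.1 reach Week 16?**
- SAP 5.2.1 uses the term key secondary endpoints, defined there as those evaluated at Week 24, to limit the supplementary and sensitivity analyses. SAP 6.4 does the same for subgroups. The MMRM sentence in 5.2.1 says secondary without that qualifier, so it covers Week 16.
- The visits entering the model run up to the analysis visit, which is not fixed at Week 24.
- SAP Section 2 says that text taken from the protocol is italicized. The primary estimand in 2.1.1 is italicized and 2.1.2 is not. The Week 16 estimand is therefore the SAP's own text rather than carried-over wording.

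**Does other text support the restriction in 6.2.2?**
- In SAP 5.1 the sentence before the promise of inference describes the MMRM as used "to estimate the difference of treatment effect between each dose of vupanorsen versus placebo at Week 24". This makes 5.1 weaker support for a Week 16 analysis than 5.2.1, but it does not restrict 5.2.1.
- The statements in SAP 5.1 and 7.2 that no testing will be done concern the interim analysis. Section 6.2.2 belongs to the final analyses.
- Appendix 1 has no Week 16 row. It also has no rows for the tertiary endpoints, which SAP 6.3.2 sends to the Section 5.2 methods, so its silence decides nothing.

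**Count of what is affected if 6.2.2 governs**
- Secondary endpoints (SAP 3.2): TG, ApoB and LDL-C at two visits (6) + non-HDL-C at Week 16 (1) + ANGPTL3 at two visits (2) = 9. Five are at Week 16 and four at Week 24.
- Vupanorsen arms (SAP Table 1): 7.
- Contrasts with placebo: 9 × 7 = 63. At Week 24, 4 × 7 = 28 have a planned difference, CI and p-value. At Week 16, 5 × 7 = 35 have none tabulated; 35/63 = 55.6%.

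**Can the planned models supply the estimate?**
All five variables already have a Week 24 MMRM with a treatment-by-visit term (SAP 5.2.1, 6.1.1.1, 6.2.1). The Schedule of Activities has lipid panel, ApoB and ANGPTL3 samples at Weeks 4, 8, 12 and 16 (4 post-baseline visits through Week 16) and at Weeks 20 and 24 (6 through Week 24). A Week 16 contrast can come from the six-visit fit or from a separate four-visit fit. The rule in 5.2.1 on which visits to include, read literally, points to the four-visit fit.

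**The case against.** The strongest reply is that 5.2.1 is general text and 6.2.2 is specific, so 6.2.2 prevails and the difference between visits is deliberate. Key secondary endpoints are the Week 24 ones, one sentence in 5.1 ties the MMRM to Week 24, and 6.2.1 grants the full analysis immediately before 6.2.2 withholds it. The SAP is also allowed to modify the protocol. This may well describe the intent and would tell a programmer what to run. It still leaves 2.1.2 defining a quantity that nothing estimates.

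A second point is that the count of 35 holds only if 6.2.2 prevails. If 5.2.1 or protocol 9.4.3 prevails, the contrasts are planned. That is correct, and the count is conditional on that reading.

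A third point is that little is lost. The planned Week 24 model contains the Week 16 contrasts, and 5.2.1 provides for plots in which "LS-Mean +/- standard error will be plotted for the observed data, (percent) change from baseline over time by treatment groups", which arguably include Week 16. The study is exploratory, without multiplicity adjustment or formal decision rules. All of this stands. It bears on importance and does not remove the conflict.

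**Conclusion.** The concern holds. SAP 6.2.2 contradicts SAP 2.1.2 and 5.2.1 and, taken as written, leaves a declared secondary estimand without its planned estimate, CI or p-value for 5 of 9 secondary endpoints (35 of 63 contrasts). The conclusion assumes that secondary in 5.2.1 carries its plain meaning from SAP 3.2 and that the count is made with 6.2.2 governing. The departure from protocol 9.4.3 is permitted, so the defect is the inconsistency within the SAP. No bias in any estimate is claimed, and the primary, Week 24 and dose-response analyses are unaffected. It should be fixed before unblinding.

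**What to change.** Replace the sentence in SAP 6.2.2 with one stating that Week 16 LS means, placebo-adjusted LS-mean differences, 95% CIs and p-values without multiplicity adjustment will be reported from the Section 5.2.1 MMRM on FAS_primary, alongside the summaries and mean plots. State whether the fit through Week 16 or the fit through Week 24 supplies them. Five Week 16 rows in Appendix 1 would help but are not essential.

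The cost is SAP wording and a few tables. No new model is needed if the fit through Week 24 is used; the fit through Week 16 needs five further MMRM fits.

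If descriptive reporting at Week 16 is what the sponsor wants, narrow SAP 2.1.2, 5.1 and 5.2.1 to match and record in the SAP the departure from protocol 9.4.1 and 9.4.3. That costs wording only. Both documents require a protocol amendment only for major changes to the primary endpoint or its analysis, so none is needed here. The choice is the sponsor's.
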